## Introduction

This document (Statistical Analysis Plan, SAP) describes the planned analysis and reporting for the clinical trial, **Mortality Reduction after Oral Azithromycin**, Contingency Study, Years 3-4, Niger. It includes specifications for the statistical analyses and tables to be prepared for the interim and final Clinical Study Report. This study is a Phase IV clinical trial to compare methods to reduce childhood mortality using mass administration of azithromycin (Pfizer, CAS 83905-01-5) compared to placebo. The content of this Statistical Analysis Plan meets the requirements stated by the US Food and Drug Administration and conforms to the American Statistical Association's Ethical Guidelines.

The following documents were reviewed in preparation of this Statistical Analysis Plan:

- Mortality Reduction after Oral Azithromycin, Protocol
- Mortality Reduction after Oral Azithromycin, Statistical Analysis Plan
- Mortality Reduction after Oral Azithromycin, Manual of Operations
- ICH Guidance on Statistical Principles for Clinical Trials

The planned analyses described in this SAP will be included in future manuscripts. Exploratory analyses not necessarily identified in this Statistical Analysis Plan may be performed to support the analysis. Unplanned analyses not delineated in this Statistical Analysis Plan will be documented as such in the final Clinical Study Report and manuscripts.

This document will be reviewed prior to the enrollment of patients. All subsequent changes will be indicated by detailed change log in the Appendix.

# MORDOR Stage 2 Contingency Study

## 1 Introduction

Should the primary analysis of azithromycin to prevent mortality reveal evidence of a benefit, we propose to proceed with two additional studies in Stage 2.

## 2 Design

Contingency study A. All communities in Niger will receive treatment at the conclusion of MORDOR Stage 1 (original study). Specifically, azithromycin communities will continue with azithromycin, and placebo communities will receive azithromycin at the 24 month visit (census number 5). Follow-up will occur at month 30 and month 36, providing one additional year of data.

Contingency study B. At the 36 month visit, rerandomization will occur, and half of communities will begin to receive placebo.

## 3 Analysis

The primary outcome is mortality, analyzed in the same way as in MORDOR Stage I, i.e., present on an initial census, and absent on the next follow-up census due to death. Since the study has been extended, the same analytic template will be used for each visit, e.g. at 48, 54, and 60 months. Each visit that is conducted will be reported.

Study A:

1. Sample size considerations.
  - a. Assuming communities of size 668 with approximately 17% in the target age range, an effect size of 20%, 10% loss to follow-up per year, 2% mortality per year, and a CV of 0.51, 312 communities per arm provides approximately 87% power (see MORDOR Phase I SAP for details).
  - b. Updating based on data from Phase I (Niger), we find the following. Assuming the observed CV of 0.34, a death rate of 2% per year results in approximately 80% power to detect a 17% effect. A death rate of 2.5% per year (and a CV of 0.34) result in approximately 80% power to detect a 15.5% effect size.
2. Primary prespecified analysis: We propose to compare the former placebo arms with the former azithromycin arms, using negative binomial regression. Significance testing is two-sided with an alpha of 0.05, and will be based on permutation testing. (This analysis is identical in every way to the country subgroup analyses conducted in Stage 1). This is restricted to the period from 24 months to 36 months, covering two six-month study intervals.

3. We propose, as a prespecified secondary analysis, a longitudinal comparison of the original placebo communities. We propose to contrast the first four study intervals during which these communities received placebo, to the last two study intervals during which these communities received azithromycin. Analysis will be conducted using negative binomial regression, with a permutation P-value reported (two-sided,  $\alpha=0.05$ ). The community-randomized nature of the trial is thus taken into account.
4. Additional supplementary analyses will be distinguished from the two prespecified analyses above. In particular, the following will be reported:
  - a. Analysis of the seasonality and timing of deaths: time of death, time of treatment for those who died, and time since treatment for all deaths. We will conduct comparisons of time since treatment conditional on death based on the Cramer-von Mises test (exactly as in Stage 1), additionally comparing across treatment arms and longitudinally. Comparisons of equality of circular means will be used to assess seasonality of death and of treatment, comparing between randomization arms and longitudinally. We will, in particular, focus special attention and reporting to a comparison of phases 1-4 to 5-6 within the placebo arm.
  - b. Analysis will be reported according to the same age classes used in the original study (Keenan et al, NEJM, 2018), i.e. 1-5, 6-11, 12-23, 24-59 months.
  - c. We will examine the difference between phase 5 and 6 in the same way.
  - d. We will report longitudinal analysis of mortality changes in the original azithromycin arm, using a linear predictor of study interval (1—6).
  - e. We will compare estimated treatment effect at a regional level using placebo mortality rates as a predictor.

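### Study A compares two arms that both receive azithromycin, so its 87% power is not power for a drug effect, and its one prespecified analysis of starting the drug cannot separate the switch from a secular trend.

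*SAP*

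**What the plan says.** SAP section 1 of the Stage 2 text makes the contingency studies conditional: "Should the primary analysis of azithromycin to prevent mortality reveal evidence of a benefit". Under section 2 the azithromycin communities continue the drug and "placebo communities will receive azithromycin at the 24 month visit (census number 5"). Protocol 17.8 also describes open-label azithromycin for all participants in the third year.

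Section 3, Study A, then gives:

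- **Item 1a (power).** For a 20% effect, 2% annual mortality and a CV of 0.51, "312 communities per arm provides approximately 87% power (see MORDOR Phase I SAP for details"). Study B repeats this text for a rerandomized placebo-versus-azithromycin contrast.
- **Item 1b (update).** At the observed CV of 0.34, about 80% power for a 17% effect (2% rate) or a 15.5% effect (2.5% rate).
- **Item 2 (primary).** "We propose to compare the former placebo arms with the former azithromycin arms, using negative binomial regression", restricted to months 24–36.
- **Item 3 (secondary).** Within the original placebo communities, the first four intervals are contrasted with "the last two study intervals during which these communities received azithromycin". A permutation P-value is reported, and the SAP adds: "The community-randomized nature of the trial is thus taken into account".
- **Item 4.** "Additional supplementary analyses will be distinguished from the two prespecified analyses above". Among the supplementary analyses, 4d reports "longitudinal analysis of mortality changes in the original azithromycin arm".

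**The concern.** Two things do not carry over from a placebo-controlled design.

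First, item 2 has no untreated arm. If the azithromycin arm stays at 1.6% per year, a 20% difference requires the former placebo arm to stay at 2.0%, which means a year of azithromycin does nothing there. The more the drug helps the newly treated arm, the smaller the difference item 2 can find. The 87% therefore should not be read as Study A's power for an azithromycin effect.

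Second, item 3 does address starting the drug, but all its communities switch at the same visit and it has no concurrent comparator. Calendar time and treatment coincide. Permutation can respect the clustering but cannot separate the two, so falling mortality could be reported as a benefit of starting, and rising mortality could hide one. The SAP mentions secular effects only in its Morbidity Study paragraph.

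**Working it through.** **Inputs from SAP Study A, items 1–3:** community size 668, 17% in the age range, 10% annual loss, 312 communities per arm, rates of 2% or 2.5% per year, CV k = 0.51 or 0.34, two-sided alpha 0.05. Item 2 covers one year. Item 3 compares two years with one.

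**Reproducing the stated power.** Child-years per community: y = 668 × 0.17 × 0.90 = 102.2. For a cluster-randomised rate comparison,

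SE² = [λ0/y + λ1/y + k²(λ0² + λ1²)] / (c − 1), power = Φ(|λ0 − λ1|/SE − 1.96).

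- Item 1a: λ0 = 0.020, λ1 = 0.016, k = 0.51. The bracket is 0.0001957 + 0.0001565 + 0.0001040 + 0.0000666 = 0.0005228. Dividing by 311 gives SE = 0.001297, 0.004/SE = 3.085 and power 87.0%.
- Item 1b, 17% at 2%: 0.0034/0.001184 = 2.871, power 81.9%.
- Item 1b, 15.5% at 2.5%: 0.003875/0.001360 = 2.849, power 81.3%.

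All three stated figures reproduce. The 87% is a one-year figure, which matches item 2's window.

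**Power by residual difference between the two treated arms** (same formula, both tails, 2% rate):

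| Residual difference | CV 0.51 | CV 0.34 |
|---|---|---|
| 0% | 5% | 5% |
| 5% | 11% | 13% |
| 10% | 32% | 38% |
| 15% | 62% | 71% |
| 20% | 87% | 93% |

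As an illustration, if starting azithromycin closed half of an assumed 20% gap, the comparison would be 1.8% against 1.6%, with power 36–42%.

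**Item 3 under a trend and no effect of switching.** Let ρ be the correlation of community effects between periods. The documents do not give it, so it is taken from 0 to 1:

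Var(log RR) = [1/(λb × 2y) + 1/(λa × y) + 2k²(1 − ρ)] / 312.

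For a 10% fall (0.020 to 0.018):

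- ρ = 1: (0.2446 + 0.5436)/312 gives SE = 0.0503. With |ln 0.9| = 0.1054, z = 2.10 and rejection is 55%.
- ρ = 0, k = 0.51: adding 0.5202 gives SE = 0.0648, z = 1.63 and rejection 37%.

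The same steps give 13–18% for a 5% fall and 92–99% for a 20% fall. Gamma-Poisson simulation with community-robust Wald tests, standing in for the permutation test, gives closely similar figures. Closed form and simulation together span about 12–19%, 37–57% and 91–99%.

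**Arm-by-period interaction.** Its variance is the sum of the two arms' variances. A proportional trend shared by both arms cancels, and simulated rejection is about 4–6%. With no trend, a 20% effect and full catch-up (2.0% to 1.6% in the former placebo arm, 1.6% throughout in the other):

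- ρ = 1: SE = √[(0.8561 + 0.9173)/312] = 0.0754, |ln 0.8| = 0.2231, z = 2.96, power 84%.
- ρ = 0, k = 0.51: SE = √[(1.7734 + 1.0404)/312] = 0.0950, z = 2.35, power 65%.

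Simulation gives about 64–85%, against 93–99% for item 3. At half catch-up the interaction has about 20–31%. Under full catch-up with a shared 10% rise in mortality, item 3 has about 51–73% and the interaction about 67–87%.

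**The case against.** A fair defence is that the SAP hides nothing. Item 2 names the arms as former placebo and former azithromycin, section 2 says both are treated, and item 1b is already worded as detectable effects. Item 2 is a valid randomised comparison of treatment histories. Item 3 is labelled longitudinal and secondary. Item 4d and Study B item 4 report trends in treated communities, and the drug itself was tested against concurrent placebo in Stage 1. Much of this stands, and it keeps the point modest. However, neither 4d nor Study B item 4 is contrasted with item 3. Study B tests withdrawal after universal treatment, not starting.

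Three stronger readings are tempting, and the documents do not support them:

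- *That the 87% was demonstrably computed for azithromycin versus placebo.* Item 1a names no contrast, and the figure is correct for any 20% difference with those inputs. That origin is inferred from the Phase I SAP reference and the repetition in Study B. The Phase I SAP is not available here.
- *That the SAP claims its permutation P-value removes secular trend.* The sentence "The community-randomized nature of the trial is thus taken into account" most naturally refers to clustering.
- *That Study A is declared to test whether the gap between arms closes, or that non-significance will be read as no drug effect.* The SAP says neither.

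**Conclusion.** The point holds in a limited form. The power arithmetic is sound. What is missing is a statement that Study A's figures are differences by treatment history between two treated arms, and any reason to expect a difference as large as 20% there. Power for smaller residuals is low: about a third for 10% and little above alpha for 5%.

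Item 3 lacks a concurrent comparator and is sensitive to quite small trends. A 10% shared fall alone makes it reject in roughly four to six trials out of ten.

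The residual differences, catch-up fractions, trend sizes and between-period correlation are assumptions, because the documents give none. The item 3 and interaction figures also rest on Wald tests and a 2% placebo rate. Neither the primary test nor item 3 needs to be withdrawn.

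**What to change.** 1. **Beside item 3**, add a supplementary negative binomial model with original arm, period (intervals 1–4 versus 5–6) and their interaction. Use community-robust standard errors or permute a studentised statistic, because Stage 1 continues to this study only if the arms differed, so exchangeability of the arms before month 24 cannot be assumed. Report it with items 3 and 4d.
2. **In item 1**, label the Study A figures as detectable differences by treatment history between two treated arms. At a 2% rate, give power at both CVs (0.51 to 0.34): about 11–13% for a 5% residual, 32–38% for 10%, 62–71% for 15% and 87–93% for 20%.
3. **In the change log** promised in the SAP's opening Introduction, record both as dated changes. Label the interaction unplanned if month-36 mortality by arm had already been seen. The resistance sample-size text already cites month-36 data and Protocol 17.8 describes year 3 in the past tense, so this would be a late clarification.

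The cost is a few sentences and one model on data already planned for collection. The stated power for Study A becomes less favourable. The interaction is weaker than item 3 when there is no trend, and it does not show which arm moved, so items 3 and 4d are still needed to read it.

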#### Study B (years two and three of mortality contingency study)

1. Sample size considerations are the same as in Study A (year 1).
  - a. Assuming communities of size 668 with approximately 17% in the target age range, an effect size of 20%, 10% loss to follow-up per year, 2% mortality per year, and a CV of 0.51, 312 communities per arm provides approximately 87% power (see MORDOR Phase I SAP for details).
  - b. Updating based on data from Phase I (Niger), we find the following. Assuming the observed CV of 0.34, a death rate of 2% per year results in approximately 80% power to detect a 17% effect. A death rate of 2.5% per year (and a CV of 0.34) result in approximately 80% power to detect a 15.5% effect size.
2. The primary prespecified analysis will contrast the rerandomized placebo arm with the rerandomized azithromycin arm. This will be conducted with negative binomial regression, using a two-sided  $\alpha$  of 0.05 and a permutation test by randomization arm.
3. Supplementary analyses will control for prior history (original randomization arm).
4. Longitudinal analysis for communities who always received azithromycin will be reported.
5. We will compare all four groups for the last year of data (two histories by two final treatments).

6. Additional analyses by the same age groups as before and by phase will be reported.
7. Models of timing, seasonality, and geography will be reported as secondary analysis.

Morbidity Study. Analysis of morbidity communities will follow the exact template as Stage I. Primary prespecified analyses will be two-sided, at an alpha of 0.05. However, the morbidity communities are still receiving placebo. Note that we will report the full follow-up at 48 months separately from the Stage 1 primary analyses. We will also look for secular effects longitudinally over the four years of the full study, as well as phases 5-8 separately.

1. Anthropometry: we will examine height and weight longitudinally, and WFH Z score secondarily. Please see the Stage 1 SAP for details.
2. Other analyses will include drug resistance and malaria, as in Stage 1.
3. Note that we do not do nares or conjunctiva swabs, conjunctival photos, or any swabs on 7-12 year olds in the contingency study.

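### Study A item 3 is a non-randomised before-after contrast, so its rate ratio cannot separate azithromycin from a common time effect, and the SAP's sentence about randomisation holds at most for clustering

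*SAP*

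**What the plan says.** SAP section 2 (Design, contingency study A) continues azithromycin in the azithromycin communities, while "placebo communities will receive azithromycin at the 24 month visit (census number 5". No staggered or randomised switch date is described.

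SAP section 3, Study A, sets out two prespecified analyses. Item 2 (primary) compares the two original arms over months 24 to 36, when both receive azithromycin. Item 3 (secondary) stays within the original placebo communities: "We propose to contrast the first four study intervals during which these communities received placebo, to the last two study intervals", the last two being on azithromycin. It uses negative binomial regression with a two-sided permutation P-value at 0.05, and concludes: "The community-randomized nature of the trial is thus taken into account".

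Item 3 names no concurrent comparator and does not say what is permuted. Study B item 2 does say, by specifying "a permutation test by randomization arm". The SAP Introduction lists "Mortality Reduction after Oral Azithromycin, Statistical Analysis Plan" among the documents reviewed. That Stage 1 plan may define the scheme, but it is not among the documents supplied.

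Item 4d separately reports a trend over the six intervals in the original azithromycin arm, as a supplementary analysis.

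**The concern.** Randomisation fixed which arm a community was in, not when it switched. Within the placebo arm, intervals 1-4 are all placebo and intervals 5-6 are all azithromycin, so one rate ratio carries both the drug and anything else that changed. A permutation confined to these communities draws no validity from the original randomisation.

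Some change over time is plausible from the documents themselves. Protocol section 17.8 describes third-year azithromycin as open label, whereas in Stage 1 the census workers were masked to arm (protocol section 5.1.1). Masking may therefore change at the same moment as treatment.

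What is at stake is interpretation. Item 2 compares two treated arms, so item 3 is the only one of the two prespecified Study A tests aimed at what happens when placebo communities start azithromycin. A reader who takes the sentence on randomisation at face value would give the result more causal weight than the design supports.

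**Working it through.** **1. Inputs (SAP section 3, Study A, item 1).** 312 communities per arm; community size 668 with 17% in the age range; 10% loss per year; 2% mortality per year; CV 0.34 (0.51 in item 1a). Person-years per community-year: 668 × 0.17 × 0.9 = 102.2.

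**2. Reproducing the SAP's power.** These figures are for the between-arm comparison; the SAP gives none for item 3. With λ₁ = λ₀(1 − effect), y = 102.2 and c = 312:

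power = Φ( (λ₀ − λ₁) / √{[(λ₀ + λ₁)/y + k²(λ₀² + λ₁²)]/(c − 1)} − 1.96 )

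- Item 1a (20% effect, 2%, CV 0.51): 0.004/0.001297 − 1.96 = 1.12, power 0.870 against the stated 87%.
- Item 1b: 0.819 (17% effect, 2%) and 0.813 (15.5% effect, 2.5%), against the stated 80%.

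The inputs are therefore read correctly, with one year of follow-up.

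**3. Bias of item 3 with zero drug effect.** Interval midpoints are 0.25, 0.75, 1.25 and 1.75 years before the switch (mean 1.0) and 2.25 and 2.75 years after it (mean 2.5), a gap of 1.5 years. A common decline of d per year gives a rate ratio of about (1 − d)^1.5.

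| Assumed d | Rate ratio | Share of a 17% effect |
|---|---|---|
| 0 | 1.000 | 0 |
| 3% | 0.97^1.5 = 0.955 | 0.045/0.17 = 26% |
| 5% | 0.95^1.5 = 0.926 | 0.074/0.17 = 44% |

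**4. Rejection by normal approximation.** Expected deaths per arm with no trend: 312 × 102.2 × 0.02 × 2 ≈ 1,276 before and 638 after. The variance of the log rate ratio is 1/before + 1/after if community effects persist fully. If they are independent by interval, add (0.34²/312)(1/4 + 1/2) = 0.000278.

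- d = 3%: deaths 1,237 and 591, SE 0.050-0.053, log ratio −0.046, rejection 14-15%.
- d = 5%: deaths 1,212 and 561, SE 0.051-0.054, log ratio −0.077, rejection 30-33%.

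Rejection reaches 10% at a decline of about 2.1-2.2% per year.

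**5. Permutation schemes, by simulation (zero drug effect, nominal 5%).**

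- *Periods permuted within community:* 4-5% with no trend, 14-17% at 3%, 27-34% at 5%. This scheme assumes no common time effect.
- *Original arm labels permuted across both arms:* 4-6% at every trend, but it uses the azithromycin arm, which item 3 leaves out.
- *One interval schedule shared by all communities:* C(6,2) = 15 assignments, smallest P = 1/15 = 0.067, so significance at 0.05 is impossible.

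The one-arm rate ratio is the same number under all three and stays confounded.

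**6. Two-arm alternative.** The arm-by-period contrast is (placebo after/before) ÷ (azithromycin after/before). With original arm labels permuted, it rejects 4-7% under zero drug effect at every trend simulated.

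Power at a true 17% effect with no trend: deaths are 1,276 and 529 in the placebo arm, and 1,059 and 529 in the azithromycin arm; |ln 0.83| = 0.186.

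- Arm-by-period: √(1/1,276 + 1/529 + 1/1,059 + 1/529) = 0.074, power 71%; with independent interval effects, SE 0.078 and power 67%. Including the simulations, about 63-73%.
- Item 3: SE 0.052-0.054, power 93-95%; including the simulations, 91-96%. This figure is valid only with no time effect.

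**The case against.** **The SAP does not call item 3 randomised.** It labels the comparison longitudinal and secondary, and for Study B it says: "The primary prespecified analysis will contrast the rerandomized placebo arm with the rerandomized azithromycin arm". The disputed sentence could mean only that analysis is at community level. This stands as to severity. It does not make the sentence accurate for the rate ratio.

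**The inflated rejection rates need two assumptions:** a trend, and within-community permutation. A reader might infer that item 3's test is known to have an inflated error rate. The documents do not support that. They give no trend and do not state the scheme, and arm-label permutation holds its level. What needs no assumption is that the one-arm rate ratio cannot identify the drug effect.

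**The two-arm model is no cure.** A reader might infer that its P-value should become the one of record for the switch. That is not supported either. Stage 2 is conditional: "Should the primary analysis of azithromycin to prevent mortality reveal evidence of a benefit". If Niger supplied between one third and all of the Stage 1 information (assumed), and Stage 1 was selected on Z below −1.96, the interaction under zero drug effect has a mean rate ratio of 0.957 to 0.907 and rejects 9-23%. Item 3 rejects 7-14% with no trend and 28-45% at a 3% yearly decline. After selection, the interaction rejects less often only if the decline exceeds about 0.6-1.2% per year, and is less biased only above about 1.5-3.3%. This stands, and it limits the model to a supportive role.

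**Its components are already planned.** On the log scale the interaction equals item 2's contrast minus the Stage 1 Niger contrast. This is correct for crude rates; only the joint estimate and test are new. Item 4d and Study B's longitudinal analyses show that time was considered, but none is joined to item 3. Both periods are whole years, so stable seasonality is nominally balanced.

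**Conclusion.** The concern holds as an identification point: item 3 is a non-randomised before-after estimate, and its sentence on randomisation is true at most for clustering. This follows from SAP sections 2 and 3 alone. The size does not: 0.955 and 0.926 rest on assumed declines of 3% and 5% per year, and the 14-17% and 27-34% rejection rates also require permutation of periods within community. Severity is minor to moderate. The SAP rests no decision on item 3, and the primary comparison in item 2 is untouched.

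**What to change.** 1. Replace the sentence on randomisation with a statement that item 3 is a non-randomised before-after estimate that accounts for clustering only and cannot by itself attribute the change to azithromycin.
2. Keep item 3 and report beside it, as supportive, a negative binomial model of both original arms with arm, period (intervals 1-4 versus 5-6) and arm-by-period. Take the interaction P-value from permuting original arm labels across communities. If the model is added after month-36 mortality data were seen, label it unplanned, as the SAP Introduction requires.
3. State that both estimates reuse the Stage 1 data that triggered Study A and can be biased toward benefit, the interaction more so when there is little or no trend. State also that the interaction reflects any change over time in the azithromycin arm, and that neither estimate replaces the Stage 1 or the re-randomised Study B comparison.

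The cost is SAP wording and one model on data that the study collects anyway. The price in precision is the interaction's lower power, about 63-73% at a 17% effect.

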1.3. Study Sites

A consortium of experienced researchers and program implementers will conduct the study in 3 sites (Malawi, Niger, and Tanzania), chosen for diversity of geography and comorbidities, existence of a functioning national azithromycin distribution program, and previous investigator experience:

- **Southern Africa:** Mangochi district, Malawi (Malawi Ministry of Health, University of Malawi, Blantyre, and London School of Hygiene & Tropical Medicine)
- **West Africa:** Loga and Boboye departments, Niger (Carter Center Niger, Niger Ministry of Health, University of California, San Francisco)
- **East Africa:** Kilosa and Gairo districts, Tanzania (National Institute for Medical Research, Kilosa, Johns Hopkins University)

Chapter 2: Context

Reduction of childhood mortality is an international development goal. The United Nations Millennium Development Goals call for a two-thirds reduction in childhood mortality by 2015.⁴ Despite progress this past decade, under-5 mortality remains unacceptably high.^{1,5,6} In Africa, where the burden of childhood mortality is greatest, three-quarters of all childhood deaths occur after the neonatal period, with malaria, pneumonia, and diarrhea accounting for the majority.⁷ Management is often case detection and individualized therapy, but novel strategies such as mass treatment may play a role.⁸⁻¹⁰

The proposed research will assess whether childhood mortality can be reduced using a novel approach – mass antibiotic administrations similar to those used for trachoma. The World Health Organization (WHO) recommends repeated annual distribution of single-dose oral azithromycin to each resident of trachoma-endemic communities, though more frequent treatments may be necessary.¹¹⁻¹³ While azithromycin effectively clears the ocular strains of chlamydia that cause trachoma,^{12,14,15} the drug also has activity against major causes of childhood mortality, including respiratory infections, diarrhea, and malaria.¹⁶⁻¹⁸ Mass treatments have been shown to be effective for these non-chlamydial infections. For example, in a study we conducted in Nepal, the prevalence of diarrhea in children decreased from 32% before a mass azithromycin treatment, to 11% ten days post-treatment (OR 0.26 [95% CI 0.14 – 0.43]).¹⁹ Others in our consortium have found that malaria parasitemia decreased by 44% after mass azithromycin treatments.²⁰ It is feasible that periodic mass

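### Item 4a tests season of death only through equality of circular means, which can detect a shift in the average date but not a smaller seasonal peak on the same date

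*SAP*

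**What the plan says.** SAP section 3, Study A, item 4a covers timing and seasonality of deaths. For seasonality it states: "Comparisons of equality of circular means will be used to assess seasonality of death and of treatment", both between arms and over time. It names no specific circular test and no method of calibration. It then undertakes to "focus special attention and reporting to a comparison of phases 1-4 to 5-6 within the placebo arm". In the original placebo communities, that sets the four placebo intervals against the two later azithromycin intervals.

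The item's one whole-distribution method is applied to a different variable: "comparisons of time since treatment conditional on death based on the Cramer-von Mises test". Time of death is also to be reported, without a stated method. Item 4 as a whole is supplementary and is to be kept apart from the two prespecified analyses.

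For Study B, item 7 says only: "Models of timing, seasonality, and geography will be reported as secondary analysis".

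**The concern.** A mean direction is an average date. It carries no information on how tightly deaths cluster around that date. Two groups can share a circular mean while one has a sharp peak and the other is nearly flat.

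Flattening is a reasonable alternative to consider here. Protocol Chapter 2 says that "the drug also has activity against major causes of childhood mortality, including respiratory infections, diarrhea, and malaria", and the protocol plans an extra blood-sampling visit in the first malaria season, which the schedule table marks as Niger only. A drug that prevents peak-season deaths makes the peak smaller; it need not move it. At stake is whether the prespecified seasonality test could register that pattern, or would return a non-significant result that could be misread as unchanged seasonality.

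**Working it through.** **Inputs.** From Study A item 1a: community size 668, 17% in the age range, 10% loss per year, 2% mortality per year, 20% effect, CV 0.51, 312 communities per arm. The level is taken from the primary analysis ("Significance testing is two-sided with an alpha of 0.05") and assumed to apply to item 4a. The documents give no seasonal amplitude, so a range is used.

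**Reproducing the plan's figure.** Child-years per community: y = 668 × 0.17 × 0.90 = 102.2. The cluster-rate formula is

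n − 1 = (z_α + z_β)² [(r0 + r1)/y + CV²(r0² + r1²)] / (r0 − r1)²

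With r0 = 0.020 and r1 = 0.016, the bracket is 0.036/102.2 + 0.2601 × 0.000656 = 0.000523. Dividing by 0.004² = 0.000016 gives 32.7. Then (z_α + z_β)² = 311/32.7 = 9.52, so z_β = 3.085 − 1.96 = 1.125 and power is 0.870. The SAP states about 87%. This supports the death counts below; the SAP states no power for seasonality.

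**Deaths in the original placebo arm.** 312 × 102.2 × 0.02 = 638 per year, so about 1,276 over phases 1–4. With a 20% reduction, phases 5–6 have 638 × 0.8 = 510.

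**Principle.** Let the density of death dates be proportional to 1 + A cos(t − μ). The mean direction is μ, the resultant length is R = A/2, and peak:trough is (1 + A)/(1 − A). If A falls while μ stays fixed, the hypothesis of equal means is true. Rejection then stays near alpha whatever the number of deaths.

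**Simulation.** 1,276 v 510 independent deaths, 1,500 to 4,000 replicates. The circular-mean test is a large-sample test that allows unequal concentration. Ranges are across repeated runs.

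| Change, mean date fixed unless stated | Circular mean | Watson U-squared |
|---|---|---|
| None (3:1 in both) | 4–5% | 5% |
| 3:1 to 1.7:1 (A halved) | 5–8% | 85–86% |
| 30% cut in peak half-year only, from 3:1 | 5–6% | 73–74% |
| 2.3:1 to 1.5:1 (A halved) | 5.8% | 66% |
| 1.9:1 to 1.2:1 (A cut by two-thirds) | 9–10% | 67–68% |
| 1.9:1 to 1.4:1 (A halved) | 6.4% | 43% |
| 1.5:1 to 1.2:1 (A halved) | 9.0% | 21% |
| 30-day shift, 3:1 in both | 92–94% | 84–85% |

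The peak-half case matches a 20% overall effect: at A = 0.5 the peak half-year holds 0.5 + 0.5/π = 65.9% of deaths, and 30% of that is 19.8%. Stronger seasons (4:1 or 9:1, halved) give U-squared 95% or more and the circular mean 5%. A two-degree-of-freedom sine/cosine test performs like U-squared throughout. Using 640 v 510 deaths leaves the circular-mean test at 4.4–9.1% when the amplitude is halved.

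**Asymmetric flattening.** Put 25% of deaths in a narrow peak lying 0, 30, 60 or 90 degrees from the main season, and remove half of that peak. The circular-mean test rejects 6%, 10%, 23% and 38%, against 57–65% for U-squared.

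**Choice of circular-mean test.** The Watson-Williams test rejects 23–63% in the halving cases, but it also rejects 11–50% with no change at all under these cosine patterns. That is loss of size, not power. Permuting group labels over individual deaths gives 8–22%.

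**The case against.** Several points on the other side stand.

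- **Consequence.** The item is supplementary and no primary or secondary mortality conclusion rests on it. A reader might infer that the trial would lose its account of why mortality fell. The documents do not support that: the SAP does not tie item 4a to protocol objective 3, which also draws on the morbidity communities and verbal autopsy. Time of death is to be reported as well, and a flatter peak could be visible there.
- **Size.** A reader might take 5–9% as the test's power against any azithromycin effect on season. It is not. It assumes flattening symmetric about the mean date, and with a true null it is essentially test size. The gain from a whole-pattern test is modest when the season is weak.
- **Attribution.** Phases 1–4 v 5–6 is a before-and-after contrast. A milder season that took peak:trough from 3:1 to 1.7:1 would make U-squared reject about 85% of the time with no drug effect. In phases 5–6 both original arms receive azithromycin, so the between-arm comparison has no placebo reference there.
- **Study B.** A reader might infer that item 7 repeats the problem. It promises models without naming any, so it is unspecified and does not exclude a treatment-by-season model.
- **Replacement.** Dropping the circular-mean test would lose some power for a pure date shift (92–94% down to 84–85%).

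These limit the consequence and shape the remedy. They do not supply a test of peak size, and item 4a has none.

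**Conclusion.** The gap is real and modest. The only inferential method named for season of death cannot detect a change in peak size that leaves the mean date alone. Under such a change rejection is about 5–9%, against about 65–85% for a whole-distribution test when the change is moderate to strong, more in very strong seasons, and about 20–45% when a weak season is halved.

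The figures assume an annual cosine pattern of unknown amplitude, symmetric flattening, independent deaths (community clustering was not modelled) and a two-sided 5% level. The structural point needs only that the mean date stays fixed. A non-significant circular-mean result should therefore not be read as evidence that seasonality is unchanged.

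**What to change.** In item 4a, keep the circular-mean test and label it as a test of date shift only. Add one prespecified whole-pattern test of date of death: Watson's two-sample U-squared, the circular counterpart of the Cramer-von Mises test already in the item, or a group-by-season sine and cosine term. Report mean direction and resultant length for each group.

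For randomised contrasts, take P from permutation of community arm labels. For phases 1–4 v 5–6 in the original placebo arm, define a within-community scheme, for example permuting whole-year blocks within each community, and state that the result remains open to calendar-year differences in season.

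Name the same test in Study B item 7, where the rerandomised placebo comparison exists.

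The cost is a few lines of SAP text and one additional supplementary test. U-squared uses dates of death already collected. The sine/cosine option, if fitted in the negative binomial model, would also need deaths and person-time split by calendar month.
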